**Aim 2c: To evaluate miRs expression to predict atherosclerosis and response**

In an exploratory analysis, similar model selection strategy as in aim 1 will be applied which will include traditional risk factors. Based on the model we generated in aim 1, we will add miRNAs as additional factors (singly and in combination). Using this model, we will be able to test the effect of miRNA(s) at baseline on the rate of atherosclerosis progression and to identify patients who demonstrate greater response (e.g. decreases in PAV). The first half of patients (n=30 per group) will be used to build our model (training stage). The rest of the patients enrolled will be used to validate this model (validation stage). Features that are dropped from the model because of redundancies will be retained for further univariate testing in the validation data. Combining biological and clinical deliberations with statistical

results will likely generate a few alternative models with similar prediction accuracy. Cross-validation will be used to evaluate a classifier's prediction accuracy and for choosing the best tuning parameters. The classifier's prediction accuracy will be the main objective of this aim. For sample size calculations, we use the method described by Dobbin et al. 183, 184, which is based on the assumption that the expected accuracy of the classifier is controlled within a percentage (tolerance) of the best possible classifier. Assuming a maximum tolerance of 5% (and at most a 2-fold difference in the differentially expressed miRNAs (assuming a median SD of 0.71), a sample size of n=60 total (training and validation sets) is required. Tolerance represents the difference in the probability of correct classification in the training sample with respect to the same probability from an optimal signature. This sample size does not guarantee that there will be differentially expressed miRNAs. Instead, this sample size will be enough to validate a differentially expressed miRNAs, if such miRNAs is found in the data. Baseline miRNAs will also be correlated with markers of alternate activation (CD206+ and CD163+ monocytes) and MR gene/protein expression.

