### Secondary Efficacy Endpoints

Change in central aortic SBP, Change in central aortic DBP, Change in central aortic Mean BP, 24-hour mean ambulatory BP, 24-hour ambulatory diastolic blood pressure, and HOMA-IR.

Evaluate miRs involved in regulating MR expression and differentially regulated miRs as predictors of disease progression and response.

Compare monocyte inflammatory activation in Spironolactone vs placebo at 6-weeks.

Investigate pre-miR/mimics and antagonomirs to regulate NR3C2 expression and alternate macrophage phenotype in human macrophages.

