**Analysis Plan:** After distributions are checked and outliers are investigated for veracity, descriptive statistics by treatment arm will be reported for patient demographics and important potential confounding variables at baseline. These will include age, gender, BMI, baseline blood pressure, HbA1c, 24-hour urine Na, plasma and renin/aldo activity at baseline, HOMA-IR, HDL and non-HDL cholesterol. To analyze these data (primary end points and secondary outcome measures), linear mixed models with group (drug/placebo), baseline plaque volume, time points (before/after), stratification variables (age, high-risk feature) and other potential confounders (such as demographics and other comorbidities) as well as a patient random effects (to account for the correlation of measures within same patient) will be used. Different covariance structures will be used and best model will be selected based on AIC criteria by first fitting most complicated mean structure model, selecting the best covariance structure, then selecting the best mean structure, using SAS procedure GLIMMIX or MIXED) and convergence and model performance will be evaluated using SAS fit statistics (e.g. AIC criteria). Clinically relevant interactions will also be included in the models. Forward stepwise selection followed by backward elimination will be used to retain features with the greatest combined prediction power while maintaining parsimony using a training data set. Traditional methods, such as AIC and BIC involve a combinatorial optimization problem, which is NP-hard, with computational time increasing exponentially with the dimensionality. The expensive computational cost makes traditional procedures infeasible for high-dimensional data analysis. To overcome this, penalized likelihood maximization and penalized risk minimization have been intensively used for classification. Penalized methods with  $L_p$ -penalty, especially when  $p \leq 1$ , automatically perform variable selection by removing predictors with very small estimated coefficients. Fan et al. proposed SCAD-penalty with better oracle properties 131 . It automatically selects features and avoids excessive estimation bias compared to  $L_1$ -penalty. We will use penalized methods for classification in order to avoid over-fitting problems by producing sparse solutions via feature selection.

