**Aim 2a: To evaluate the functional significance of candidate miRNAs.**

**Analysis Plan:** An interaction contrast in an ANOVA model will be used to test the effects of overexpression of miRNAs (miR mimic) or antagomiRs in various experiments where we will test the effect of miRNAs alone or in the presence of LPS or IL4/13. The effect of various interventions on NR3C2 gene expression and MR protein expression as well as markers of alternate activation will be tested.

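### Aim 2c names no treatment-by-miRNA contrast, so it cannot tell miRNAs that predict benefit from spironolactone from those that predict PAV change equally in both arms

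*Combined protocol and SAP*

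**What the plan says.** The heading of Aim 2c gives two purposes: "To evaluate miRs expression to predict atherosclerosis and response". The Secondary Efficacy Endpoints section repeats both, listing "differentially regulated miRs as predictors of disease progression and response".

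The method is short. Aim 2c is labelled exploratory and takes over the Aim 1 approach: "In an exploratory analysis, similar model selection strategy as in aim 1 will be applied which will include traditional risk factors". To the model from Aim 1, "we will add miRNAs as additional factors (singly and in combination". That one model is then meant to test the effect of baseline miRNAs on the rate of progression and "to identify patients who demonstrate greater response (e.g. decreases in PAV". The training set has 30 patients per group, so it includes both arms. The rest are for validation, and classifier accuracy is the stated main objective.

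The Aim 1 analysis plan describes "linear mixed models with group (drug/placebo), baseline plaque volume, time points (before/after" and further covariates, with a patient random effect. It adds: "Clinically relevant interactions will also be included in the models". It does not say which. The text that follows describes forward stepwise selection, backward elimination and penalised methods that remove predictors with small coefficients.

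For the laboratory work in Aim 2a the plan is explicit: "An interaction contrast in an ANOVA model will be used to test the effects of overexpression of miRNAs". Aim 2c has no corresponding sentence.

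**The concern.** A marker of response to a drug is one for which the difference between drug and placebo depends on the marker's value. A marker of progression is one that goes with PAV change whatever the treatment. Only a treatment-by-marker contrast tells them apart.

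Aim 2c does not name that contrast, and its one example of response is a change within the patient. On that description a placebo patient whose plaque shrinks is a responder, and a miRNA that goes with slower progression in both arms alike could be reported as a predictor of response to spironolactone. A miRNA with opposite associations in the two arms, which is strong evidence of differential benefit, could be missed because its average effect is near zero.

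The stake is one stated secondary endpoint. The Study Rationale presents prediction of response as one of several innovations and as input to a later definitive trial. Carrying a prognostic marker forward as a predictive one would misdirect that design. The primary PAV comparison is not affected.

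**Working it through.** **1. What the text fixes and leaves open.**

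| Question | Progression | Response |
|---|---|---|
| Promised in Aim 2c and the secondary endpoints | yes | yes |
| Contrast needed, before/after mixed model | miRNA-by-time | group-by-time-by-miRNA |
| Contrast needed, model of PAV change | miRNA | group-by-miRNA |
| Contrast named in Aim 2c | none; miRNAs are added factors | none |
| Protected from selection | not stated | not stated |

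**2. The plan's own figure.** Inputs from the Aim 1 section: CV 0.83, 1.5-fold difference, 80% power, α = 0.05; tests are two-sided. The log-scale SD is √ln(1 + 0.83²) = 0.724 and the difference is ln 1.5 = 0.405. The noncentral t calculation gives 52 per group, as stated, and 104/0.8 = 130. So 52 per arm and SD 0.724 are a sound basis for what follows.

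**3. A purely prognostic miRNA.** Assumptions: one marker, correlation r with PAV change, the same in both arms; model with group and marker; two-sided 0.05. With N patients in total, the chance that the marker term is significant is about Φ(atanh(r)·√(N − 4) − 1.96). For r = 0.3, atanh(r) = 0.3095.

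- 52 per arm, N = 104: 0.3095 × 10 − 1.96 = 1.135, so 87%. Simulation gives 87%.
- 30 per arm, N = 60: 0.3095 × 7.483 − 1.96 = 0.356, so 64%. Simulation gives 64 to 65%.
- Significance in both stages, 30 per arm for training and 52 − 30 = 22 per arm for validation: the second stage (N = 44) gives 0.3095 × 6.325 − 1.96 = −0.003, or 50%. Jointly 0.639 × 0.499 = 32%. Simulation gives 33%.

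At 52 per arm with a single test, the range is 53% for r = 0.2 to 99% for r = 0.4. The group-by-marker test flags the same markers in about 5% of trials, its nominal error rate, because there is no interaction to find.

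**4. A miRNA with opposite associations by arm** (−0.3 and +0.3, 52 per arm). Simulation: the additive test flags it in 6% of trials, close to chance. The interaction test flags it in about 87%. Check: (2 × 0.3095)/√(2/49) − 1.96 = 3.064 − 1.96 = 1.104, so 87%.

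**5. Power of the missing test.** SD 0.724, one miRNA, no multiplicity correction; the interaction sizes are assumptions.

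- Median split, 1.5-fold ratio of treatment ratios, 52 per arm (four cells of 26): SE = 0.724 × √(4/26) = 0.284; 0.405/0.284 − 1.96 = −0.53, so about 30%. At 30 per arm, about 19%.
- Continuous miRNA, treatment ratio changing 1.5-fold per SD, 52 per arm: SE = 0.724 × √(2/52) = 0.142; 0.405/0.142 − 1.96 = 0.90, so about 81%. At 30 per arm, about 58%. This assumes that one SD of the marker shifts the treatment ratio by as much as the whole effect for which the trial is sized.

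**The case against.** **The plan does not say main effects only.** A reader might infer that Aim 2c commits to main effects. The documents do not support that. The wording is additional factors, the Aim 1 model contains group, and interactions are allowed for. The main-effects reading also fits badly: in a before/after model a miRNA main effect concerns PAV level, whereas Aim 2c speaks of rate of progression. This stands. A treatment-by-miRNA term is permitted. But it is not named, and selection could remove it. Aim 2c keeps features dropped as redundant for univariate testing in the validation data, but that is not stated to include the interaction.

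**Half of the aim is openly prognostic and all of it is exploratory.** This stands too. For progression, flagging a prognostic miRNA is the right result. Exploratory status lowers the standard of evidence, but it does not turn a test of progression into a test of response.

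**An additive model is not blind to predictive markers.** A reader might infer that it finds prognostic markers only. That is too strong: with a marker active only in the drug arm (an assumed 1.5-fold change per SD), the additive model flagged it in about 75% of simulated trials at 52 per arm. It cannot show that the marker is predictive.

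**The 87% is not an error rate of the planned analysis.** Correct. It is the power of one test of one marker in all completers, at an assumed correlation. The plan splits the patients and judges classifier accuracy. Requiring significance in both stages lowers the figure to about 33%, still well above 5%.

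**A detailed SAP is still to come.** The Statistical Methods section says so. That makes the change easy; it does not supply the contrast.

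**Conclusion.** The point holds as a gap in prespecification. Aim 2c promises predictors of response, names no treatment-by-miRNA contrast, and illustrates response by PAV decrease alone. As written it cannot separate miRNAs that predict benefit from those that predict PAV change equally in both arms. Under the assumptions in the working, a purely prognostic marker at r = 0.3 is flagged in about 87% of trials (52 per arm), about 65% (30 per arm) or about 33% (both stages required), against about 5% with the interaction test. The direction of this result does not depend on the chosen correlation; the size does.

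The documents do not show that interactions are ruled out, that the progression half of the aim is wrong, or that the trial's rationale as a whole fails. Imaging coverage, macrophage polarization and the use of monocyte miRNAs are separate innovations that this leaves untouched.

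**What to change.** In the SAP still to be written:

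1. Name the treatment-by-miRNA contrast as the test of response: group-by-time-by-miRNA in the before/after mixed model, or group-by-miRNA in a model of PAV change adjusted for baseline.
2. Keep that contrast and its lower-order terms in the model, outside stepwise and penalised selection.
3. Test progression separately, by the miRNA-by-time effect averaged over arms. In a model of PAV change, use centred treatment coding or an additive model. With 0/1 coding and the interaction present, the miRNA coefficient is the slope in the reference arm only.
4. Define any responder rule by the predicted difference between spironolactone and placebo, and train and validate it on that, not on PAV decrease pooled over arms.
5. Report response findings as exploratory, with confidence intervals, and state the power.

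The cost is wording: no new patients, visits or assays. The drawback is limited power, about 30% at 52 per arm in the median-split case and lower in the training half. Using the miRNA as a continuous variable helps. Fewer predictors of response will be declared, but those declared will address the question asked.

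### Aim 2c takes classifier accuracy as its main result but specifies no accuracy for the same model without miRNAs, so that figure alone cannot show that the miRNAs predict

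*Combined protocol and SAP*

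**What the plan says.** Statistical Methods and Considerations, Aim 2c, describes an exploratory analysis. On how the model is formed it says "similar model selection strategy as in aim 1 will be applied which will include traditional risk factors" and "Based on the model we generated in aim 1, we will add miRNAs as additional factors". The Aim 1 analysis plan gives the content of that base model: "linear mixed models with group (drug/placebo), baseline plaque volume, time points (before/after), stratification variables (age, high-risk feature", followed by demographics, comorbidities and other potential confounders.

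Aim 2c plans a test of the miRNA terms: "we will be able to test the effect of miRNA(s) at baseline on the rate of atherosclerosis progression". On performance it says "Cross-validation will be used to evaluate a classifier's prediction accuracy and for choosing the best tuning parameters", and then "The classifier's prediction accuracy will be the main objective of this aim". The first half of the patients (30 per group) trains the model and the rest validate it. Features dropped as redundant are kept for univariate testing in the validation data.

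The question this serves is listed under Secondary Efficacy Endpoints, which names "differentially regulated miRs as predictors of disease progression and response"; the Secondary Objectives contain a matching item. No section gives a reference accuracy, whether from the model without miRNAs, from arm alone or from the majority class. The class to be predicted is not defined.

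**The concern.** The accuracy of a classifier measures everything in it. If treatment group, baseline plaque and risk factors are in the model, the headline accuracy mixes their contribution with that of the miRNAs, and nothing planned separates the two on the accuracy scale. A more effective drug would raise the accuracy whether or not the miRNAs carry information.

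Cross-validation and the validation half protect against overfitting. They do not attribute the result: an honest out-of-sample accuracy is still the accuracy of the mixture. The protocol's Summary presents the prediction of response as input to the design of later event-driven trials, so accuracy wrongly credited to miRNAs could mislead that design.

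**Working it through.** **Inputs from the plan.** Aim 1 and Table 7: CV 0.83, two-sided alpha 0.05, 80% power, 1.5-fold difference, 52 per group, 20% loss, 130 recruited. Aim 2c: 30 per group for training. Allocation is 1:1.

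**Assumptions.** The class is above or below the median of PAV change, since none is defined. Risk factors explain a share R² of the within-arm variance, varied from 0 to 0.35. Arm and risk factors remain in the classifier.

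**Step 1: reproduce Table 7.** Log-scale SD = √ln(1 + 0.83²) = 0.724. The difference is ln(1.5) = 0.405. The noncentral-t calculation gives 52 per group and matches all nine cells of the table. Completers: 130 × 0.80 = 104. With 60 used for training, 104 − 60 = 44 remain for validation.

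**Step 2: ceiling from arm alone.** With a median split and equal arms, the best accuracy from arm is Φ(d/2), where d is the standardised difference.
- 1.5-fold: d = 0.405/0.724 = 0.560; Φ(0.280) = 61.0%.
- 2-fold: d = 0.693/0.724 = 0.957; Φ(0.479) = 68.4%.

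**Step 3: ceiling from arm plus risk factors, no miRNA information.** Simulation of 1,000,000 patients per setting, scored with the true coefficients:

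| Drug effect | R² = 0 | 0.10 | 0.20 | 0.35 |
|---|---|---|---|---|
| none | 50% | 60% | 65% | 70% |
| 1.5-fold | 61% | 64% | 67% | 72% |
| 2-fold | 68% | 69% | 71% | 75% |

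**Step 4: what to expect at the planned size.** The ceilings ignore estimation error. A second simulation (3,000 runs per setting, 60 training and 44 validation patients) fitted arm plus five risk factors, then the same model plus three pure-noise miRNAs chosen from 31 by their training correlation. Mean validation accuracy at the 1.5-fold effect:

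| R² | Without miRNAs | With useless miRNAs | Difference (points) | Share of trials with the full model above chance (one-sided 0.025) |
|---|---|---|---|---|
| 0 | 55.0% | 53.1% | −1.9 | 7% |
| 0.10 | 59.5% | 56.7% | −2.8 | 15% |
| 0.20 | 63.2% | 60.1% | −3.1 | 27% |
| 0.35 | 68.3% | 64.9% | −3.4 | 51% |

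A model with the noise miRNAs alone gives 50%. With no drug effect and R² = 0, the full model also gives 50%. The difference column is negative throughout, which is the right answer for useless miRNAs. The full-model accuracy on its own does not show it.

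**Step 5: precision of the comparison.** For paired predictions on 44 patients with little true difference, the 95% half-width is about 1.96 × √(discordant share/44). At an assumed 10% discordant it is 1.96 × √(0.10/44) = 9.3 points; at 30% it is 1.96 × √(0.30/44) = 16.2 points.

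**The case against.** The strongest reply is that the plan already contains an adjusted miRNA analysis. The build is nested, the effect of baseline miRNAs on progression is tested with arm and risk factors in the model, and the selection carried over from Aim 1 can drop uninformative miRNAs. This stands, and it rules out the reading that Aim 2c has no comparison of any kind. It does not fill the gap: a test of association is not the stated main objective, and it does not say how much of the reported accuracy the miRNAs supply.

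A second reply concerns size. A reader might infer that useless miRNAs would be reported with accuracy well above chance. The documents do not support that. The 61% and 68% figures are ceilings, and the fold differences are detectable effects from a power table, not forecasts. With 44 validation patients, at least 29 correct (66%) are needed to exceed 50% at one-sided 0.025. At 1.5-fold, a model with useless miRNAs passes that mark in 7% to 27% of trials for R² up to 0.20, and in about half only at R² = 0.35.

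Third, it is an inference that arm enters the classifier. Aim 2c refers back to the Aim 1 model but lists no classifier features, and its sample-size inputs (2-fold miRNA difference, SD 0.71) describe a miRNA signature. Selection could also drop base terms. If the class were response among spironolactone patients only, arm would carry no information, although risk factors and baseline plaque still could. The point is therefore conditional.

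Finally, the aim is exploratory and a detailed SAP is still to be written. That limits the weight of the point and also makes it easy to settle.

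**Conclusion.** The point holds in a conditional form. Aim 2c's main result is an absolute accuracy for a model that, as described, extends one containing treatment group, baseline plaque and confounders, and no accuracy without miRNAs is specified beside it. If those terms stay in, accuracy may exceed chance with no contribution from the miRNAs: roughly 53% to 65% on average in validation at the 1.5-fold effect. This range rests on the median split, on R² between 0 and 0.35, and on the 60/44 division. The last is itself a reading, because Aim 2c also calls 60 the total for training and validation together. With no drug effect and uninformative risk factors the figure is 50%.

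The accuracy cannot by itself show that miRNAs predict progression or response. No primary conclusion depends on this, but it should be corrected because the main result does not isolate the question the aim asks.

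**What to change.** In the SAP, fit the Aim 1 model without miRNAs and the same model with them on the same training patients, and score both on the same validation patients. Make the difference in out-of-sample performance, with its confidence interval, the main Aim 2c result. Show the full classifier's accuracy only beside that reference. The SAP should also define the class to be predicted and state whether arm and risk factors are kept in the classifier, since the size of the problem depends on both.

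The cost is one extra model fit and some SAP wording, with no new data. The headline figure will be smaller. The interval will also be wide, with a half-width of about 9 to 16 points for 44 validation patients and 10% to 30% discordant predictions. The comparison may often be inconclusive, and the SAP should say so in advance.

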## CRITERIA FOR EVALUATION

### Co-Primary Efficacy Endpoints

The co-primary outcome measure is change in 24-hour SBP in Spironolactone treated patients versus placebo and percent change in total atheroma volume (PAV) in thoracic aorta of Spironolactone vs placebo.

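### Exploratory Aim 2c makes classifier accuracy its main objective, but the outcome (change in PAV) is continuous and no class or cut is defined

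*Combined protocol and SAP*

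**What the plan says.** Aim 2c, under Statistical Methods and Considerations, opens as exploratory: "In an exploratory analysis, similar model selection strategy as in aim 1 will be applied". It gives the miRNAs two uses. One is to extend the Aim 1 model so as to "test the effect of miRNA(s) at baseline on the rate of atherosclerosis progression". The other is to "identify patients who demonstrate greater response (e.g. decreases in PAV"). The section then states that the classifier's "prediction accuracy will be the main objective of this aim". Its sample size of 60 rests on a tolerance of 5% in the probability of correct classification, a two-fold difference in miRNA expression worded as an upper limit, and a median SD of 0.71.

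The imaging endpoint is continuous. The co-primary endpoint section defines it as "percent change in total atheroma volume (PAV) in thoracic aorta of Spironolactone vs placebo", and the Aim 1 analysis plan uses "linear mixed models with group (drug/placebo), baseline plaque volume, time points (before/after"). That same plan adds: "We will use penalized methods for classification in order to avoid over-fitting problems". Neither section says what the classes are.

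**The concern.** A classifier needs classes. The only hint of one is the example of a decrease in PAV, which comes without a cut-point, a number of classes or an expected prevalence. Two things follow.

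- The declared main objective is not defined. Accuracy depends on where the cut falls as well as on the miRNAs, and with nothing fixed in advance the cut could be chosen after the data are seen.
- The natural way to make classes is to split change in PAV at one point, which throws away information on how much each patient changed. The aim has about 104 evaluable patients, and the pilot array carried more than 600 miRNAs, so it has little information to spare.

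The sample-size statement adds a smaller fault. A size that is adequate for a two-fold difference is not adequate for every smaller one, so wording two-fold as a maximum reverses the assumption.

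**Working it through.** **Inputs from the documents.** 52 evaluable patients per group, 104 in all, and 130 recruited with 20% loss (Aim 1). Classifier n=60, tolerance 5%, two-fold difference, SD 0.71 (Aim 2c). The section gives 60 as the total for training and validation and also, as 30 per group, for training alone. Pilot miRNA–plaque r² runs from 0.15 to 0.36 (Preliminary Studies); it relates to baseline plaque in a derivation cohort of 10, not to change.

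**Inputs assumed.** Roughly normal change in PAV; r²=0.15 (the low end of the pilot range) and, as a more cautious value, r=0.3; one test at two-sided 0.05.

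**1. The plan's own figures.** On the log scale SD = √ln(1+0.83²) = 0.724. A noncentral-t calculation then gives 52 per group for a 1.5-fold difference at 80% power, as in Table 7, and 104/0.8 = 130. The classifier's n=60 cannot be checked, because the number of miRNAs p, the number of informative ones m and the class prevalence are missing. I therefore varied them, with d the standardised difference:

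- best possible accuracy = Φ(d√m/2);
- accuracy at n = the maximum over selection level a of Φ{(d/2)·m·power(a,n)/√(m·power(a,n)+(p−m)·a)};
- required n = the smallest n with a gap of at most 0.05.

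On the log2 scale d = 1/0.71 = 1.41. With p=600 and m=1, the required n is 44 at 50/50 prevalence, 52 at 30/70 and 65 at 20/80. The undefined class alone moves n across the stated 60.

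**2. Direction of the two-fold assumption.** With p=600, m=1 and balanced classes:

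| d | reading | required n |
|---|---|---|
| 1.41 | two-fold, log2 scale | 44 |
| 0.98 | two-fold, natural log (ln 2/0.71) | 75 |
| 0.82 | 1.5-fold, log2 scale (0.585/0.71) | 95 |

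Over this range a smaller difference needs more patients, so the planned difference has to be a minimum.

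**3. Information kept by one cut at quantile q.** Efficiency = φ(z_q)²/{q(1−q)}.

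| Cut | Efficiency | Loss | 60 patients count as |
|---|---|---|---|
| 50/50 | 0.3989²/0.25 = 0.637 | 36% | 38 |
| 30/70 | 0.3477²/0.21 = 0.576 | 42% | 35 |
| 25/75 | 0.3178²/0.1875 = 0.539 | 46% | 32 |
| 20/80 | 0.2800²/0.16 = 0.490 | 51% | 29 |

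The median is the best case, so 36% is the minimum loss for any single cut.

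**4. Power for one miRNA.** Power ≈ Φ{atanh(r)·√(n−3) − 1.96}. A median split shrinks r by √(2/π) = 0.798.

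| r | n | Continuous | Median split |
|---|---|---|---|
| 0.387 (r²=0.15) | 60 | Φ(3.085−1.96) = 87% | r=0.309: Φ(2.412−1.96) = 67% |
| 0.387 | 104 | Φ(4.107−1.96) = 98% | Φ(3.211−1.96) = 89% |
| 0.3 | 60 | Φ(2.337−1.96) = 65% | r=0.239: Φ(1.843−1.96) = 45% |
| 0.3 | 104 | Φ(3.111−1.96) = 88% | Φ(2.453−1.96) = 69% |

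Simulation at r²=0.15 and n=60 agrees: 86% continuous, 68% with a median split and 60% with a 25/75 split.

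**The case against.** Several points on the other side stand.

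- **No cut is stated.** The loss is therefore conditional. Classes formed from the extreme thirds, with the middle dropped, would lose about 21%. The plan does not propose this, but does not exclude it.
- **The aim also uses the continuous outcome.** A reader might infer that Aim 2c as a whole discards a third of its information. The documents do not support that: the extended Aim 1 model tests miRNAs against continuous progression.
- **The power figures concern association, not accuracy.** They show what splitting costs when one miRNA is tested. They do not measure lost classifier accuracy.
- **Identifying responders is a stated purpose.** Fixing the class and cut in advance would close the definitional gap. It would not recover the lost information.
- **The aim is exploratory and a detailed SAP is still to be written.** The primary comparison is untouched.

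A reader might also infer that the classifier scores scan noise as response, since with no mean change half the patients would show a decrease (31% if mean progression were 0.5 SD of change). Those shares are simply the part of a normal distribution below zero, and would be the same with perfect measurement. Mislabelling depends on the reliability of change in PAV, which is not given. About a median cut it is arccos(√reliability)/π: 10% at an assumed reliability of 0.9 and 25% at 0.5.

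**Conclusion.** The point holds for the classifier objective and its sample size, and no further. The main objective of Aim 2c is the accuracy of a classifier whose classes are undefined, for an outcome that the plan measures and elsewhere models as continuous. Under any single cut of a roughly normal change in PAV, the classifier loses at least 36% of the information. At a median cut this is a fall in single-miRNA power of about 20 percentage points at n=60, and of 9 to 19 points at n=104, for assumed r between 0.39 and 0.3. These figures rest on normality, one test at 0.05 and assumed correlations; the documents give no correlation between miRNAs and change in PAV. The stated n=60 cannot be verified without the class prevalence and the number of miRNAs, and its two-fold assumption is worded in the wrong direction. This is a worthwhile, inexpensive improvement to an exploratory aim and does not threaten the primary result.

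**What to change.** In the SAP:

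1. Make the main objective of Aim 2c the out-of-sample prediction error (mean squared error or R²) for continuous exit PAV, adjusted for baseline PAV and arm. Keep the SCAD penalty named in Aim 1, with squared-error loss.
2. Include miRNA-by-arm terms wherever response to the drug is claimed. Aim 2c names none, and without them the model predicts progression, not response to treatment.
3. Show any responder classification only as a secondary display, with the number of classes and the cut fixed before data are examined.
4. If the classifier sample-size statement is kept, change at most to at least for the two-fold difference, and state the number of miRNAs and the class prevalence.

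No new data are needed. The downside is that the classification-tolerance justification for n=60 no longer applies and must be replaced by a statement of the precision with which prediction error or R² will be estimated. Interaction terms also add coefficients to a small data set, so claims about response to drug will be less precise than claims about progression.
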